2.0 Add Department(s)				
2.1 List departments associated with this study:				
Primary Department Name				
● GW - SCHOOL OF NURSING RESEARCH				

	Affiliation:	Note: Non-GW team members should only be included on this list if they are not listed on an IRB approved protocol at their own institution or organization. An Institutional Authorization Agreement or Independent Investigator Agreement will be needed for these individuals.	
	Conflict of Interest - Do you have any outside interests related to this research (ex: personal stock in the company sponsoring the research, receipt of income, including royalties and entitlement to royalties, from the sponsor of this research for purposes other than this research, etc.) that could possibly be perceived as introducing bias into the research or as a conflict of interest?	C Yes © No	
	Date added to research team:  Date removed from research	01/25/2019	
	team:		
5.0		Review Determination	
5.1	Are you applying for an Exempt stu	ady?	
(	⊃ Yes ⊙ No		
5.2	Please indicate which of the categor	ries below describe this study:	
	Minimal Risk Greater than Minimal Risk		
6.0	)	GW's Role	
6.1	Select GW's Role in the Project:		
(		involved in this study) d will rely on another IRB for review) d each site is doing their own review)	
6.2	Is GW acting as a data coordinating	g site?	
(	Yes O No		
7.0		Funding	
7.1	Is this study externally funded?		

400		$\sim$	
100	Yes	- 100	No

#### 7.2 Provide the following information for each individual funding source:

Note: attach a copy of each grant, sub-award, contract, etc. in the Initial Review Submission
Packet so the IRB can compare the aims outlined in the funding document scope of work with the
research protocol. (If your funding source documents are over 200 pages, include only the cover
page and the applicable sections of the funding source documents as they relate to this new IRB
application or existing IRB file.)

View Details Sponsor Name			Sponsor Type	Contract Type:	Project Number	Award Number
	Gordon and Betty Moore Foundation		Nonprofit	Contract		
Sponsor	Name:	Gordon and Betty Moore Foundation				
Sponsor	Type:	Non	profit			
Sponsor	Role:	Fun	ding			
Grant/Co	ontract Number:					
Project F	Period:	Fror	n:11/01/2018 to:10/31/2018			
Is Institu	ution the Primary Grant	No				
Contract	Type:	Con	tract			
Project N	lumber:					
Award N	umber:					
Grant Tit	le:					
PI Name (If PI is r on the st	not the same as identified					
Significa	nt Discrepancy:					

### 8.0

#### **Objectives and Justifications**

#### 8.1 Summary of the study using lay language (200 words or less):

The Pathways Collaborative is the first attempt to implement supportive (palliative) kidney care at multiple sites in the United States. While supportive kidney care is growing in other countries, notably Canada, Australia, and Great Britain, it is not yet known how to integrate it into the unique nephrology environment in the United States. In Phase 1 of Pathways (completed), we developed an evidence-based change packet of 14 best practices for integrating supportive care practices into the continuum of care for patients with end stage renal disease (ESRD). In Phase 2 (described in this application), we will conduct a learning collaborative to help up to 15 dialysis centers and associated CKD practices implement these best practices. The learning collaborative is based on the IHI Collaborative Model for Achieving Breakthrough Improvement. This model is a tested systematic approach to quality improvement designed to help organizations close the gap between current and future practice based on evidence-based best practices. [i]

The Pathways Project faculty will work with up to 15 change teams at dialysis centers and associated CKD practices to create a system to identify seriously ill patients with kidney disease; conduct conversations with them so that their values, preferences, and goals for current and future medical treatment are known and respected; assess and address patients' physical, psychological and spiritual needs; and coordinate care throughout the healthcare system so patients receive only the care they want in settings in which they wish to be.

[i] Nadeem E, Olin SS, Hill LC, Hoagwood KE, Horwitz SM. Understanding the components of quality improvement collaboratives: A systematic literature review. *Milbank Q*. 2013;91(2):354-394. doi:http://dx.doi.org/10.1111/milq.12016.

[ii] Wells S, Tamir O, Gray J, et al. Are quality improvement collaboratives effective? A systematic review. BMJ Quality and Safety. 21 October 2017. doi. 10.1136/bmjqs-2017-006926

#### 8.2 Objective(s) and justification of the study including the purpose, research question(s), hypothesis and relevant background information:

#### Aim 1: Hold Breakthrough Collaborative for integrating supportive care into kidney care

To achieve an overall improvement in aligning treatment with patient values and preferences, satisfaction with care, quality of life, and symptom and pain management, Pathways Project Collaborative teams will embark on an 18-month Collaborative beginning spring 2019. The Collaborative will be preceded by a 4-month observation period to obtain baseline measurements of current dialysis center and associated CKD practices supportive care practices. Through the application of the Pathways Project change package, project teams will enhance the delivery of supportive care processes for patients with kidney disease, specifically through the testing and implementation of shared decision-making and advance care planning; systematically identifying seriously ill patients; and providing palliative dialysis to seriously ill patients with advanced CKD whose goals are not compatible with standard dialysis schedules.

#### Aim 2: Revise Pathways change package and resources in preparation for dissemination

In summer 2020, the Pathways Project Advisory Committee, including patient subject matter experts, will revise and strengthen the change package, resources and tools based on the knowledge gained through the Collaborative. The revisions will incorporate the dialysis center/CKD teams' experience during the collaborative along with the preliminary evaluation results.

#### Aim 3: Develop strategy for dissemination

In fall 2020, the Pathways Project Advisory Committee will develop a strategy to disseminate the revised change package and results of the Collaborative. The dissemination strategy will include outreach to three audiences based on the outcomes of the Pathways Project: 1) the professional and scientific community through presentations at national meetings and articles in peer-reviewed journals; 2) the large dialysis organizations and those who oversee quality of dialysis care including the Forum of ESRD Networks, the individual networks, and the American Health Quality Association; and 3) policy makers including members of Congress and CMS to advocate for changes to improve patient-centered care for patients with kidney disease.

To achieve these aims we will employ three primary tactics:

- 1) The IHI Breakthrough Collaborative Model The Collaborative Model is the primary intervention for this project. It has been used to foster successful change adoption in numerous settings with a variety of health problems.
- 2) Integrated payment models. Integrated payment models realign financial incentives to create a fertile field for uptake of innovations in patient- and family-centered care in the kidney care continuum. Several of the sites participate in the ESCO Model (ESRD Seamless Care Organizations) which is a pilot program being conducted by CMS to test value-based payment models for dialysis care. At least four of the participating dialysis centers are part of the ESCO demonstration. Three centers (at [REDACTED], ) are part of a similar private initiative to provide an integrated care model for ESRD patients. The site within the Veterans Administration also works within the financial system of the VA, which is a budget based model, rather than service reimbursement model.
- 3) The Pathways Change Package Provides an evidence-based set of changes and tools collated from the research literature and experiences and efforts of exemplars and organizations that have already successfully adopted supportive care best practices and shown positive outcomes.

Justification for the study: ESRD patients have significant unmet palliative care needs and arguably are the chronic disease patient population who receive the worst end-of-life care because of high intensity care (intensive care unit admission with frequent cardiopulmonary resuscitation, mechanical ventilation and feeding tube use compared to patients with cancer and other chronic diseases) at the end of life with very low referral to hospice. They have a high symptom burden, multiple comorbid illnesses, and a shortened life expectancy.

Hypothesis: A collaborative quality improvement approach with training of independent dialysis centers and associated CKD practices in supportive care best practices will lead to improvements in patient and staff-reported outcomes in patient care.

Research Question: Will a collaborative quality improvement approach to spreading supportive care best practices at dialysis centers and affiliated clinics measurably increase the provision of supportive care best practices leading to more effective goal-concordant care?

#### Relevant background information:

The absence in the United States of a comprehensive medical management without dialysis pathway which is available and selected by about 15% of advanced chronic kidney disease (CKD) patients in other countries is a major deficit in U.S. kidney care. In other ways as well, the current care of patients with advanced CKD in the U.S. is not patient-centered, nor does it utilize supportive care approaches to optimize patients' quality of life. The Pathways Project is seeking to address these deficits through the implementation of a Collaborative.

In a 2013 survey of dialysis center staff, only 4.5% of 487 respondents believed they were presently providing high-quality supportive care including at the end-of-life. When asked what one change could most improve supportive care in their dialysis center, the top choice was "guidelines to help with decision-making in seriously ill patients." The second most frequently selected choice was the availability of supportive care consultation to patients. With the exception of a few innovative practices, specialty supportive care consultations are not generally available to patients on dialysis. In those places where supportive care consultation is an option for seriously ill patients on dialysis, nephrologists and their teams typically have not been trained in eliciting shared decision-making, communication, and symptom management skills that would help them deliver primary supportive care.

Shared decision-making is a necessary component to informed consent for patients with advanced CKD. The American Society of Nephrology (ASN) has recommended shared decision-making prior to the initiation of dialysis. Despite ASN's recommendation, shared decision-making—the process in which patients and their family collaborate with healthcare providers to develop a care plan and make decisions about treatments based on patient preferences and values as well as the clinical risks and advantages—is poorly integrated into the care of patients with kidney disease. Most nephrologists express lack of comfort in discussing end-of-life issues. Consequently, most patients with CKD and those on dialysis have little awareness of their prognosis.

Patients older than 75 years are the fastest growing segment of the dialysis population, but these patients, especially if they are frail or have comorbidities, may not experience a survival benefit from dialysis treatment. The current default is to start elderly patients with advanced kidney disease and multiple comorbid conditions on dialysis irrespective of their prognosis or likelihood of benefit. The symptom burden for patients with advanced CKD is comparable to that for patients on dialysis, and symptoms are underrecognized and undertreated because of lack of nephrology clinician expertise in supportive care.

The symptom burden of patients on dialysis rivals that of those with cancer, and their five-year survival rate is worse. This tremendous suffering leads to staggering rates of voluntary dialysis withdrawal as high as 35% in the oldest groups, yet hospice and supportive care are underutilized. As a result, patients on dialysis are subjected to more aggressive treatment at the end-of-life than patients with other serious illnesses. Most patients die in the hospital and often after intensive procedures including mechanical ventilation, feeding tube placement, and cardiopulmonary resuscitation. Families of deceased dialysis patients rate the quality of their loved ones' end-of-life care worse than families of those with cancer and other chronic conditions.

There is an urgent need to improve the care of patients with advanced and end stage renal disease (ESRD). The current situation offers the opportunity to intervene with multiple evidence-based supportive care best practices to transform the care of these seriously ill patients by improving the delivery of supportive care throughout the continuum of kidney disease and making available to seriously ill patients who wish to withdraw from dialysis, delay dialysis, or avoid dialysis, a pathway that offers medical management without dialysis.

 In surveys of patients and physicians, they prefer the term supportive care over palliative care. The term palliative care will be used to refer to the specialist title of physicians with board certification in hospice and palliative medicine along with specialist palliative care teams and to the practice of "palliative dialysis" which has a particular definition in the literature. Primary supportive care includes basic communication and symptom management skills provided by other than specialty-trained clinicians.

#### 8.3 Describe how the research results will be used and will contribute to generalizable knowledge:

The overall aim of supportive kidney care is to improve the patient and family experience by shaping care to meet patient-defined goals and preferences, especially toward the end-of-life. This is expressed in the short-hand term "goal-concordant care." This short phrase is an umbrella for a complex array of actions including patients having insight into their values, preferences, and goals; clinicians eliciting and listening to those preferences; the healthcare system offering choices that assist patients in achieving their goals;

and all parties flexibly responding as healthcare needs and corresponding patient preferences evolve. This Collaborative phase of the Moore Foundation grant will provide knowledge on how best to implement comprehensive kidney supportive care delivery in the United States. The following bullet points describe the overall, immediate, and long-term projected impact of this knowledge.

Addressing the absence of comprehensive kidney supportive care delivery in the U.S. would lead to goal-concordant care, and thus improved quality of care, reflected in the following ways:

- Patients' preferences for future care would be more systematically elicited through shared decisionmaking and advance care planning;
- Patients' high symptom burden would be addressed through the routinization of pain and symptom assessment and management using validated tools and best practice recommendations;
- Patients' quality of life, experience of care, and satisfaction with care would improve as their treatment becomes more aligned with their preferences;
- The high intensity of care at the end-of-life would decrease and more patients would die outside the hospital and at home with hospice, which is what most patients say they prefer; and
- The high cost of end-of-life care for patients with kidney disease would decrease.

The immediate impact of the Collaborative's uptake of the change package will result in:

- Nephrology clinicians trained in communication skills for shared decision-making and advance care planning;
- Nephrology clinicians trained in pain and symptom assessment and management;
- Nephrology practices developing a medical management without dialysis pathway;
- Dialysis centers including a palliative dialysis option for patients near the end-of-life;
   and Nephrology practices and dialysis centers engaging in collaborative efforts with palliative care
   and hospice programs for seriously ill patients with CKD and ESRD.

The potential longer-term impact could result in:

- More patients reporting end-of-life care discussions with their nephrologist and other clinicians;
- More patients with advanced CKD choosing medical management without dialysis (literature from other countries suggests there could be a five-fold increase);
- More patients choosing palliative dialysis;
- More patients referred to palliative care and hospice; and
- Patients reporting a higher quality of life because of better pain and symptom assessment and management.

# 8.4 How will the data be analyzed to answer the research question? Briefly describe the data analysis procedures (e.g., statistical tests, thematic analysis, factors to be compared):

Briefly describe statistical tests, thematic analysis, and the factors to be compared.

Univariate and bivariate statistics will be used to analyze outcomes. Differences between categorical variables will be analyzed with the chi-square test and between continuous variables with the t-test. Trends over time in utilization measures will be analyzed with ANOVA.

To improve the efficiency of the design, given existing limitations, the "post" intervention sample will be matched to the pre-sample in term of cluster size and pre-treatment variables that affect the outcomes of importance.

The effect of the intervention will be measured as the difference between matched clusters (post intervention minus pre-intervention) in outcome changes over the 18-month study period from pre-intervention to post-intervention. Negative differences will indicate lower outcomes post-intervention, adjusted for baseline measures. A one-sample two sided t test with corresponding confidence interval will be used to determine whether the mean difference as calculated over all matched pairs is statistically different from zero. A nonparametric permutation test will also be used with an exact p-value. We will follow the same approach for secondary outcomes on which we have appropriate pre-intervention data. To adjust the mean rate difference in (the primary outcome) between groups for variables that show some residual imbalance after the post-intervention cluster pair-matching, a multiple linear regression model will be used, with the difference between matched clusters within dialysis centers as the dependent variable and variables with pre-intervention differences between matched clusters as the independent variables. Adjusted inferences for the effect of the intervention will be estimated by calculating the intercept of the resulting regression equation and comparing it to its estimated standard error.

Donner A, Klar N: Design and Analysis of Cluster Randomization Trials in Health Research. New York: Wiley; 2000. Section 6.3.3.	

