#### D.Facility monthly report of utilization statistics

Formative evaluation - monthly reports during 18 months of the collaborative.

To assess interim progress of sites in implementing changes, each change team will submit a monthly report providing aggregate monthly information on utilization indicators such as the number of patients assessed as seriously ill, number of patients with completed advance directive, number of patients using hospice. (See attached in study documents).

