#### D. Facility-level monthly report of utilization statistics

One report per dialysis center or associated CKD practice will be obtained monthly. These reports cover all patients at the site, but data is only reported in aggregate.

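### Utilization trends are assigned to an ANOVA of unstated form; read as the usual test over 18 months it ignores month order and has less power than a slope test for a steady change

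*Combined protocol and SAP*

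**What the plan says.** The method for utilization trends is a single sentence in section 8.4: "Trends over time in utilization measures will be analyzed with ANOVA". Nothing there states whether time enters as a factor or a number, whether a contrast is planned, or whether site is in the model.

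The series that fits this sentence is described in section 9.1 D: "Formative evaluation - monthly reports during 18 months of the collaborative". Its purpose is given as "To assess interim progress of sites in implementing changes, each change team will submit a monthly report". Section 10.1 D adds the unit of data: "One report per dialysis center or associated CKD practice will be obtained monthly", and "These reports cover all patients at the site, but data is only reported in aggregate". Section 8.1 gives the number of sites: "The Pathways Project faculty will work with up to 15 change teams at dialysis centers and associated CKD practices". So there is one site-level figure per measure per month, with the same sites reporting throughout.

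The research question in section 8.2 has a direction: whether the approach will "measurably increase the provision of supportive care best practices leading to more effective goal-concordant care".

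The intervention effect is handled elsewhere in section 8.4, by a two-sided one-sample t test and an exact permutation test on post-minus-pre differences between matched clusters.

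**The concern.** A trend is an ordered, directional change. The usual ANOVA with month as a factor has a different null: all monthly means are equal, against any departure. A steady rise, a steady fall, a hump in the middle and one odd month all count alike.

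Two misreadings follow. A significant result could be reported as progress when it reflects a season, a holiday period or a reporting artefact common to the sites. A non-significant result could be reported as no progress when the sites were improving steadily, because one degree of freedom of signal is spread over 17. Adding a site term does not remove either problem. At stake is what the project says about how well sites took up the change package during the 18 months.

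**Working it through.** **Inputs.** 18 monthly reports (9.1 D); up to 15 sites, taken as 15 (8.1); one aggregate report per site per month (10.1 D). The documents give no alpha, SD, effect size or power for the utilization trend, so there is no planned figure to reproduce. Assumed: alpha 0.05 two-sided; independent normal residuals with within-site SD *s*; the same trend at every site. The total rise *R* over the 18 months is scanned in units of *s*.

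**1. Order of the months.** With site as a block, F = [15 × Σ(month mean − grand mean)² / 17] / residual mean square, on 17 and 17 × 14 = 238 df. The sum is unchanged by relabelling the months. On simulated data, shuffling the calendar left F at 1.2453.

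**2. Power for a steady rise.** The slope is *R*/17 per month and Σ(month − 9.5)² = 484.5, so the noncentrality is λ = 15 × (*R*/17)² × 484.5. For *R* = 0.6: 15 × 0.0012457 × 484.5 = 9.05. Noncentral F and t then give:

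| Total rise (SD) | λ | Omnibus F(17, 238) | t test on 15 site slopes (14 df) | Linear contrast F(1, 238) |
|---|---|---|---|---|
| 0.3 | 2.26 | 11% | 29% | 32% |
| 0.5 | 6.29 | 25% | 65% | 70% |
| 0.6 | 9.05 | 37% | 80% | 85% |
| 0.7 | 12.32 | 51% | 90% | 94% |
| 1.0 | 25.15 | 89% | above 99% | 99.9% |

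The omnibus test reaches 50% power at λ = 12.11, that is at *R* = 17 × √(12.11 / (15 × 484.5)) = 0.69.

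**3. Rejection with no linear trend.** For a U-shaped pattern common to all sites with SD 0.2, λ = 15 × 18 × 0.2² = 10.8, and the omnibus test rejects about 44% of the time. With SD 0.3, λ = 24.3 and it rejects about 87%. In simulation, a 9-month cycle of amplitude 0.3 SD gave 50% and a single odd month of +1 SD gave 58%, both after removal of any linear component. The slope test stays at about 5% in all of these. With no month effects, both tests hold about 5%. The pattern sizes are assumptions.

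**4. Where the gap narrows (*R* = 0.6; slope test 80% for the steady rise).**
- Three six-month blocks: block means are 0.6 × 6/17 = 0.212 apart, λ = 15 × 6 × 2 × 0.212² = 8.07 on F(2, 28), power 67%.
- Two nine-month blocks: difference 0.6 × 9/17 = 0.318, λ = 15 × 9 × 0.318²/2 = 6.81 on F(1, 14), power 68%.
- A rise completed over the first four monthly steps, then flat: omnibus 33%, slope test about 46%.

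**5. Site term left out.** At *R* = 0.56, where the site-blocked omnibus test has 32% power and a linear contrast 80%, a one-way ANOVA without site has simulated power of 12%, 0.8% and 0% for between-site SDs of 0.5, 1 and 2 within-site SDs.

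**The case against.** The strongest reply is that section 8.4 does not fix the form of the ANOVA, in a form field that asks only for a brief description. A linear contrast within a repeated-measures ANOVA is a valid trend test with one degree of freedom. Nor does the sentence name the 18 months as its levels: utilization data are also collected in the 4-month baseline and 4-month follow-up periods (9.1 E). With only two periods and a site term, F equals t squared and the objection about order disappears. This stands. The order-blind test is the default reading, not a stated choice. It supports asking for the test of time to be named, because leaving it open permits a choice after the data are seen.

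A reader might infer that ANOVA would miss most steady improvements. The documents give no SD or effect size to support that. It is true only below about 0.69 SD with 18 levels, and power is 89% at 1.0 SD. A reader might also infer that ANOVA turns noise into trends. It does not; only real month effects shared by the sites do this.

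The slope test is not immune either. Random month shocks of SD 0.2 to 0.3 common to all sites make it reject about 12% to 19% of the time, against roughly 41% to 79% for the omnibus test. The large power gap is also its best case, since it assumes a straight line and independent errors.

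**Conclusion.** The point holds in a conditional form. The plan pairs a question about trend with a method whose default version does not test trend, and it does not state the version that would. If month is an 18-level factor, a steady rise of 0.6 within-site SD is detected with about 37% power, against 80% for the slope test. Shared, trendless month patterns can produce frequent rejections. These figures rest on 15 sites, alpha 0.05, independent equal-variance errors and parallel trends, none of which the documents establish for these measures.

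A reader might take this as a flaw in the test of the intervention effect. The documents do not support that: the effect is tested separately on matched-cluster differences, and the monthly reports are labelled formative. The change is worth making because it is cheap and gives a direction and a size, but the study's main conclusion does not depend on it.

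**What to change.** Replace the ANOVA sentence in section 8.4 with wording such as:

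*For each utilization measure, a slope on month (numeric, 1 to 18) is fitted to each site's monthly rate. The mean slope over sites is tested with a two-sided one-sample t test and reported as change per month with a 95% confidence interval. Monthly means are plotted. Any ANOVA over months is descriptive and is not used to claim a trend.*

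A mixed model with numeric month and random site intercept and slope, testing the month coefficient, would serve equally. Reducing each site to one slope also respects the repeated reports from the same site and reuses a test already in the section.

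The cost is one sentence and no new data. A straight-line slope is less sensitive to a non-monotone course or an early rise that levels off; the plot is there to show these. Shocks common to all sites remain a limitation and should be acknowledged when the slopes are reported.
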